9.2.5 Study Drug Exposure and Compliance

Study drug exposure (in days) will be calculated as (last date of dosing – first date of dosing) + 1, regardless of study drug interruption, and will be summarized descriptively based on the Safety Set by group and overall. It will also be summarized in categories: \leq 7 days, $>$ 7 to \leq 28 days, $>$ 28 days to \leq 6 weeks, $>$ 6 to \leq 12 weeks, $>$ 12 to \leq 24 weeks, $>$ 24 to \leq 48 weeks, and $>$ 48 weeks, using counts and percentages.

Study drug compliance will be calculated as $100 \times [1 - (\text{total number of days of study drug interruption}) / (\text{duration of study drug exposure in days})]$. A study drug interruption on a given day is defined as any interruption of the study drug on that day. A study drug interruption that continues through the end of study participation (i.e., subject does not resume study drug before the end of study participation) will not be included in the compliance calculation. Study drug compliance will be summarized descriptively based on the FAS by group and overall. It will also be summarized in categories: $<80\%$ and $\geq80\%$, using counts and percentages.

9.2.6 Important Protocol Deviations

An important protocol deviation (IPD) is a deviation that may significantly affect the completeness, accuracy, or reliability of the study data or that may significantly affect a subject's rights, safety, or well-being. IPD rules will be developed and finalized before the clinical database lock. IPDs will be identified by the PD review team according to the protocol deviation plan.

IPDs will be summarized descriptively based on the FAS by group and overall.

9.3 Efficacy Analysis

All efficacy analyses described in this section will be based on the FAS, unless otherwise specified.

9.3.1 Analysis of Primary Efficacy Variable

The primary efficacy endpoint is the change from baseline in blood levels of functional AAT at Week 48.

According to CSP (V2.0), [REDACTED]

[REDACTED]

9.3.2 Analysis of Secondary Efficacy Variables

In this analysis, if the measured functional AAT levels are below the lower limit of quantification (LLOQ) of 2.77 μ M, the LLOQ value will be imputed for analysis purposes; if the measured functional AAT levels are above the upper limit of quantification (ULOQ) of 25.6 μ M, the ULOQ value will be imputed for analysis purposes.

If the measured antigenic AAT levels are below the LLOQ of 2.63 μ M, the LLOQ value will be imputed for analysis purposes; if the measured antigenic AAT levels are above the ULOQ of 45 μ M, the ULOQ value will be imputed for analysis purposes.

If the measured blood Z-polymer levels are below the LLOQ of 0.469 mg/L, the LLOQ value will be imputed for analysis purposes; if the measured blood Z-polymer levels are above the ULOQ of 2000 mg/L, the ULOQ value will be imputed for analysis purposes.

If the measured liver Z-polymer levels are below the LLOQ, the LLOQ value will be imputed for analysis purposes; if the measured liver Z-polymer levels are above the ULOQ of, the ULOQ value will be imputed for analysis purposes.

	Percent Stain Area: (unit = %)	H-Score: (unit = none)	Globule Density: (unit = number of globules/mm ²)
LLOQ	0.000%	0	0
ULOQ	100.000%	300	1000000

According to CSP (V2.0), “*There will be no further screening or enrollment, and no further study drug dosing, based on Sponsor decision to stop dosing in this study as of 25 September 2023.*” No subjects have had any post-treatment liver biopsy. The secondary endpoints related to liver Z-polymer will not be analyzed.

The observed values and change from baseline of the other secondary endpoints (functional AAT, antigenic AAT, and blood Z-polymer) will be summarized descriptively by group and overall at each visit.

9.3.3 Multiplicity Adjustment

There will be no multiplicity adjustment performed in the analysis of this study.

9.4 Safety Analysis

Safety is one of the secondary objectives of this study. All safety analyses will be performed based on the Safety Set by group and overall.

The overall safety profile of VX-864 will be assessed in terms of the following safety and tolerability endpoints:

- Incidence of treatment emergent adverse events (TEAEs)
- Clinical laboratory values (i.e., serum chemistry, hematology, coagulation, and urinalysis)
- Standard 12-lead ECG outcomes
- Vital signs
- Pulse oximetry
- Physical examination

Only descriptive analyses of safety will be performed, and no statistical hypothesis testing will be performed.

9.4.1 Adverse Events

AEs will be coded using MedDRA. AEs will be classified as pretreatment, treatment-emergent, or post-treatment as follows:

Pretreatment AEs: AEs that occurred before the first dose of study drug

Treatment-emergent AEs: AEs that worsened (either in severity or seriousness) or started on or after the first dose date of study drug through the end of the TE Period

Post-treatment AE: AE that worsened or that was newly developed after the TE period

For AEs with completely missing or partial start dates, if there is no clear evidence that the AEs started before or after the first dose of study drug, the AEs will be classified as TEAEs.

Imputation rules for missing or partial AE start dates are defined as Appendix C.

The number and percentage of subjects experiencing TEAEs will be summarized by the MedDRA SOC and PT. AE summary tables will be presented only for TEAEs by group and overall and will include the following:

- Overview of TEAEs
- All TEAEs
- TEAEs by strongest relationship
- TEAEs by maximum severity
- TEAEs leading to death
- Serious TEAEs
- Related TEAEs
- TEAEs leading to treatment discontinuation
- TEAEs leading to treatment interruption

When summarizing the number and percentage of subjects with an event, subjects with multiple occurrences of the same AE or a continuing AE will be counted once. Only the maximum severity level will be presented in the severity summaries, and the strongest relationship level in the relationship summaries.

In addition, listings containing individual subject level AE data at different course of the study treatment (pre-treatment, under-treatment, and post-treatment) for all deaths, SAEs, treatment discontinuations, and treatment interruptions will be provided separately.

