7.1 Overall Design

This is a Phase 2, open-label, multicenter study. Approximately 20 subjects with the PiZZ genotype will be enrolled. Groups A and B will enroll approximately 10 subjects each. All subjects will receive VX-864 500 mg every 12 hours (q12h) for 48 weeks. Figure 7-1 displays the study design.

Group A subjects will not have a liver biopsy.

Subjects in Group B will have 2 liver biopsies performed over the course of the study. All liver biopsies will be performed percutaneously. All subjects in Group B (approximately 10 subjects) will have a liver biopsy during the Pretreatment Interval (Figure 7-1). Approximately 5 subjects (Group B1) will have a second liver biopsy at Week 24. Approximately 5 subjects (Group B2) will have a second liver biopsy at Week 48.

The pretreatment liver biopsy must be performed at least 7 days before Day 1 dosing, after all eligibility criteria have been met. Local laboratory hematology and coagulation results must be collected and reviewed by investigator within approximately 48 hours prior to the liver biopsy being performed. The Week 24 and Week 48 liver biopsies will be performed 3 hours (± 30 minutes) postdose relative to the morning dose.

The Safety Follow-up Visits are required for all subjects. For subjects who terminate their participation early, the ETT visit, which may be conducted at the site or by telephone or video interview, replaces the Day 28 Safety Follow-up Visit, if the ETT Visit occurs 3 weeks or later following the last dose of study drug. All subjects may also consent to the posttreatment Telemedicine Visit(s) following final dose of study drug, to monitor for development of AEs of rash (for up to 6 months) and to monitor any ongoing AEs of rash (for up to 6 months following resolution of AEs of rash; see Protocol Section 9.1.6).

Figure 7-1 VX22-864-108 Study Design

Treatment Period		
Day 1 to Week 48, VX-864 (N=20)		
Screening Up to 70 days before first dose ^a	Group A (n=10) No liver biopsy	Safety Follow-up 14 and 28 (± 2) days after last dose, and posttreatment telemedicine visit(s) ^c
Group B Pretreatment Interval Up to 14 days ^b before first dose	Cohort B1 (n=5) Liver biopsy at Pretreatment Interval and Week 24	
	Cohort B2 (n=5) Liver biopsy at Pretreatment Interval and Week 48	

[figure not shown]
n: size of subsample; N: number of subjects

Notes: Figure is not drawn to scale. Figure is not drawn to scale.

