^a In subjects not requiring augmentation therapy washout, the Screening Period will be up to 28 days. In subjects requiring augmentation therapy washout, the Screening Period will be up to 70 days.

^b Day -14 to Day -7; pretreatment liver biopsy must be performed at least 7 days before Day 1 dosing.

^c There will be no further dosing in this study as of 25 September 2023. All subjects may consent to the posttreatment Telemedicine Visit(s) following final dose of study drug, to monitor for development of AEs of rash (for up to 6 months) and monitor any ongoing AEs of rash (for up to 6 months following resolution of AEs of rash; see Protocol Section 9.1.6).

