9 STATISTICAL ANALYSIS

9.1 General Considerations

The Schedule of Assessments is provided in Section 3 of CSP. The precision standards for reporting safety variables are provided in an internal Biometrics document that specifies the programming rules including the precision for derived variables.

Continuous variables will be summarized using the following descriptive summary statistics: the number of subjects (n), mean, SD, median, minimum value (min), and maximum value (max).

Categorical variables will be summarized using counts and percentages.

Baseline value, unless specified otherwise, will be defined as the most recent non-missing measurement (scheduled or unscheduled) collected before the first dose of study drug. For ECGs, the baseline value will be defined as the average of the non-missing pretreatment measurements (triplicate) on Day 1. For subjects who have ever been on augmentation therapy at any time, only functional and antigenic AAT levels collected during screening >42 days after the last dose of augmentation therapy can be used to define baseline values.

Change (absolute change) from baseline will be calculated as post-baseline value – baseline value.

Treatment-emergent (TE) Period will include the time from the first dose of study drug to 28 days after the last dose of study drug or to the completion of study participation (as defined in Section 9.1.8 of CSP), whichever occurs first.

Visit Window: The analysis visit windows for the protocol-defined visits are provided in Appendix A.

Unscheduled visits: Data obtained from unscheduled visits will be included in the analysis as follows:

- In scheduled visit windows per specified visit windowing rules
- In the derivation of baseline and last on-treatment measurements
- In the derivation of maximum and minimum values during TE period, and maximum and minimum change from baseline values during TE period for safety analyses
- In individual subject data listings as appropriate

Incomplete or missing data will not be imputed, unless specified otherwise.

Outliers: No formal statistical analyses will be performed to detect and/or remedy the presence of statistical outliers, unless specified otherwise.

All individual subject data will be presented in individual subject data listings based on the All Subjects Set.

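### TEAE tables show only crude percentages although dosing stopped on one calendar date, so they do not describe risk by time on drug

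*SAP*

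**What the plan says.** The planned treatment is in SAP 7.1: "All subjects will receive VX-864 500 mg every 12 hours (q12h) for 48 weeks". Note c to Figure 7-1 in the same section then records the stop: "There will be no further dosing in this study as of 25 September 2023".

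Time at risk for a TEAE follows dosing. Under SAP 9.1, "Treatment-emergent (TE) Period will include the time from the first dose of study drug to 28 days after the last dose of study drug". The window closes sooner if a subject's participation ends before that.

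SAP 9.4.1 gives the summary measure: "The number and percentage of subjects experiencing TEAEs will be summarized by the MedDRA SOC and PT". It adds that "AE summary tables will be presented only for TEAEs by group and overall and will include the following", followed by a list of tables (overview, all, by relationship, by severity, serious, related, leading to discontinuation, and so on). A subject with repeated occurrences counts once. Subject-level listings are also planned. Neither the readable SAP nor protocol 12.3.4 plans a person-time rate or a time-to-event summary of adverse events.

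Two other passages bear on the point. SAP 9.2.5 reports exposure in days and in categories, "regardless of study drug interruption, and will be summarized descriptively based on the Safety Set by group and overall". SAP 9.3.2 adapts the efficacy analysis to the stop: "No subjects have had any post-treatment liver biopsy", so the liver endpoints are dropped, and the other secondary endpoints are summarised descriptively. The adverse event section has no matching change.

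**The concern.** When subjects enter on different dates and all stop on one, treated time depends on entry date. The TE Period shortens with it. A percentage of all treated subjects then mixes people observed for different lengths of time. It is neither a risk at a stated time on drug nor a rate.

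Safety and tolerability is a secondary objective. With the liver endpoints gone, it is a larger share of what the study can report. Timing matters most for rash, which protocol 9.1.6 follows for up to six months after the last dose or after resolution. A reader who wants to know how rash risk builds up with weeks on drug cannot get that from the planned tables.

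**Working it through.** **No stated figure to reproduce.** The documents give no adverse event rate or precision. Their only design calculation concerns functional AAT and has no bearing here. What follows is an illustration on assumed risks and dosing lengths.

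**Inputs.** From the documents: 48 weeks planned dosing and a 28-day tail, so a full TE Period of 48 + 4 = 52 weeks; about 10 subjects per group. Assumed: a 52-week risk p (30% unless stated), the shape of the hazard, and the weeks of dosing.

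**Step 1: constant hazard, fixed dosing length.** λ = −ln(1 − p)/52. For p = 0.30, λ = 0.3567/52 = 0.00686 per week. The expected crude percentage after d weeks of dosing is 1 − exp(−λ(d + 4)).

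| 52-week risk | d = 12 | d = 24 | d = 36 | d = 48 |
|---|---|---|---|---|
| 10% | 3.2% | 5.5% | 7.8% | 10% |
| 30% | 10.4% | 17.5% | 24.0% | 30% |
| 50% | 19.2% | 31.1% | 41.3% | 50% |
| 80% | 39.1% | 58.0% | 71.0% | 80% |

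**Step 2: staggered entry, p = 0.30.** With dosing spread evenly, time at risk runs evenly from a to b weeks (dosing plus 4), and the expected percentage is 1 − [exp(−λa) − exp(−λb)]/[λ(b − a)].
- Dosing 2–24 weeks (a = 6, b = 28): 1 − (0.9597 − 0.8253)/0.1509 = 10.9%.
- Dosing 12–40 weeks (a = 16, b = 44): 1 − (0.8961 − 0.7395)/0.1921 = 18.5%.

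**Step 3: other hazard shapes, same 30% at 52 weeks.**
- No risk until Week 8, then constant (−ln 0.7/44 = 0.00811 per week): 7.0% and 16.2%.
- All risk in the first four weeks: 30% and 30%. The crude percentage loses nothing.

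**Step 4: groups with the same hazard but different exposure.** From step 1, 24 v 12 weeks of dosing gives gaps of about 2, 7, 12 and 19 points at 52-week risks of 10, 30, 50 and 80%. For 36 v 12 weeks the gaps are about 5, 14, 22 and 32 points. With equal exposure the gap is zero.

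**Step 5: would a person-time rate solve it?** First events per 100 subject-weeks, time censored at first event, for the two exposure spreads of step 2:

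| Hazard | 2–24 weeks | 12–40 weeks |
|---|---|---|
| Constant | 0.69 | 0.69 |
| After Week 8 only | 0.42 | 0.58 |
| First 4 weeks only | 2.41 | 1.39 |

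The rate is equal across exposures only under a constant hazard. For early-onset events it creates a gap that the crude percentage does not have. A Kaplan-Meier estimate needs no assumption about the shape of the hazard.

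**Step 6: chance.** With 10 per group and an equal true risk of 30% or 50%, two independent binomial counts differ by 2 or more (20 points) with probability 46% or 50%.

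**The case against.** The case for leaving the tables alone has five parts.

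- **The crude percentage is not wrong.** SAP 9.4 asks for descriptive incidence and rules out hypothesis tests. Nothing says that the tables estimate a 48-week risk. This stands: the percentage is correct for the exposure received. A reader might infer that the plan understates event risk in general. The documents do not support that; the shortfall is only against the planned duration, and only for events that keep accruing.
- **A Group A versus B artefact is hypothetical.** A reader might infer a false group difference. No comparison is planned, the groups are not randomised and have different age and FEV1 limits, and no exposure by group is given. Step 6 shows that a gap would be weak evidence in any case. This stands.
- **The evidence on exposure is indirect.** The SAP 9.2.5 categories, up to more than 48 weeks, cover the planned range and say nothing about actual spread. Missing post-treatment biopsies suggest that Group B dosing generally ended before the scheduled biopsies. They do not prove that every Cohort B1 subject had under 24 weeks: the Week 24 window is ±14 days, and a biopsy can be missed. This also stands, although staggered entry with a common stop makes unequal exposure very probable.
- **Exposure is already reported by group, and listings cover about 20 subjects.** This helps, but only in part. A dosing-duration table is not TE time at risk, and it does not place events in time.
- **Rates bring their own artefact.** Step 5 confirms this, so rates should not be the main remedy.

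**Conclusion.** The point holds as a limit on interpretation, not as an error in the tables. The SAP adapted its efficacy analysis to the stop but left the TEAE summaries as they would be for a completed 48-week study. For steadily accruing events, an assumed 52-week risk of 30% would show as about 11% to 18.5% under the two exposure spreads tried, and as about 7% to 16% with onset only after Week 8. For events confined to the first four weeks there is no loss. These sizes rest on assumed risks, hazard shapes and dosing lengths. The documents supply none of them, so neither the actual shortfall nor the size or direction of any group difference can be computed. The change is a cheap improvement, most useful for rash.

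**What to change.** In SAP 9.4.1:

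1. Keep n (%) in all TEAE tables.
2. Show median and total subject-weeks in the TE Period beside the percentages, by group and overall.
3. Add Kaplan-Meier cumulative incidence, with numbers at risk and 95% confidence intervals, for time from first dose to first treatment-emergent rash and to first TEAE. Censor at the end of the TE Period. Present it overall, and by group as description only. Do not extend the curve beyond observed follow-up.
4. Rates per 100 subject-weeks are optional. If given, label them as assuming a constant hazard.

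**Cost.** A short SAP amendment before database lock, or an entry in the clinical study report after it, as SAP section 4 allows, plus a few outputs. First and last dose dates and adverse event start dates are already collected. Intervals will be wide with about 20 subjects. The estimate also assumes that censoring is unrelated to the event. That is plausible for a common calendar stop, less so for subjects who left treatment individually; the SAP attributes the stop to a sponsor decision without giving the reason. The output should state this assumption.

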9.4.2 Clinical Laboratory

All statistical analyses of laboratory values will be performed using SI units. The observed values and change from baseline values of the continuous hematology, chemistry, and coagulation results will be summarized by groups at each visit.

The number and percentage of subjects with chemistry, hematology and coagulation values meeting threshold analysis criteria during the TE period will be summarized by group. The threshold analysis criterion shift from baseline will also be summarized descriptively. The threshold analysis criteria are provided in Appendix D.

In addition, listings containing individual subject hematology, chemistry, and coagulation values outside the reference ranges during the TE Period(s) will be provided. These listings will include data from scheduled and unscheduled visits.

Results of urinalysis and the serum pregnancy test will be listed in individual subject data listings only.

9.4.3 Electrocardiogram

For the treatment-emergent ECG measurements, a summary of observed values and change from baseline values will be provided by group at each visit and time point, as applicable, for the following ECG measurements: RR interval (msec), PR interval (msec), QT interval (msec), QTcF interval corrected by Fridericia's formula (msec), QRS duration (msec), and heart rate (beats per minute).

The number and percentage of subjects meeting threshold analysis criteria during the TE Period will be summarized by group. The threshold analysis criteria are provided in Appendix D.

In addition, the number and percentage of subjects by maximum treatment-emergent value of QT/QTcF intervals, categorized as ≤ 450 msec, > 450 msec and ≤ 480 msec, > 480 msec and ≤ 500 msec, and > 500 msec, as well as maximum treatment-emergent increase from baseline value of QT/QTcF intervals, categorized as > 30 and ≤ 60 msec, and > 60 msec and maximum treatment-emergent decrease from baseline value of QT/QTcF intervals, categorized as ≥ 30 msec, will be provided based on scheduled and unscheduled 12 lead ECG measurements.

Since ECGs are performed in triplicate, the mean of the ECGs will be used as the ECG value for summaries of observed values and change from baseline values, and all reported ECGs will be used to conduct threshold analyses.

9.4.4 Vital Signs

For the treatment-emergent vital signs measurements, the observed values and change from baseline values will be summarized by group at each visit and time point. The following vital signs parameters will be summarized: systolic and diastolic blood pressure (mm Hg), pulse rate (beats per minute), body temperature (°C), and respiratory rate (breaths per minute).

The number and percentage of subjects meeting threshold analysis criteria during the TE Period will be summarized by group. The threshold analysis criteria are provided in Appendix D.

9.4.5 Pulse Oximetry

For the treatment-emergent pulse oximetry measurements of the percentage of oxygen saturation, the observed values and change from baseline values will be summarized by group at each visit.

9.4.6 Spirometry

Spirometry results, including FVC (L), FEV₁ (L), and percent predicted FEV₁ (ppFEV₁, %), will be presented in an individual subject data listing only. The guideline for calculating ppFEV₁ is provided in Appendix E.

9.4.7 Physical Examination

Physical examination (PE) results will be presented in an individual subject data listing only.

10 INTERIM AND IDMC ANALYSES

10.1 Interim Analysis

Interim analyses (IA) may be performed at any time at the discretion of the sponsor for internal decision-making.

Interim analyses will be based on all data included in the IA data cuts.

10.2 Independent Data Monitoring Committee Analysis

Not applicable.

11 REFERENCES

Not applicable.

